## 5.3 Analysis Plan

A detailed analysis plan is described in a separate SAP. This section summarizes the main considerations for data analysis.

The key analyses for this study are the comparisons reflected by the primary and secondary aims; both intent-to-treat (as the primary) and a per-protocol approach will be used.

## 5.3.1 Primary Aims

Standard comparisons of characteristics between groups will be conducted at baseline. It is anticipated that the randomization scheme will balance the groups for these covariates (considering the large sample size) and they will not be adjusted for in the primary analyses. However, secondary analyses of relevant outcomes using regression adjustments will be implemented to account for any suggested confounding covariates that are unbalanced between study groups. The potential adjustment covariates include baseline BP level, race/ethnicity, smoking status, prior anti-hypertensive use (known CHTN), gestational age at baseline and weight. Per protocol analyses, which reflect adherence to antihypertensive therapy will be conducted in secondary analyses.

The primary analysis will compare the incidence of the composite outcome and SGA between the 2 study groups – a chi-square p-value and the RR and 95% CI (relative to ACOG comparison group) will be computed and followed up with a logistic regression comparison which will take into account the duration of therapy, GA at initiation of therapy and other covariates. Event free survival will be calculated using Kaplan Meier estimates and tested using a log rank test. Student's t-test comparisons of continuous outcomes (duration of hospital, NICU stay, etc.) will be conducted.

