#### 1.3a Secondary Aims/Hypotheses related to the primary hypothesis include the following:

- a) To better quantify the risks of severe maternal cardiovascular outcomes associated with mild CHTN during pregnancy and determine the impact of treatment.
- b) To test whether antihypertensive (compared to withholding therapy) reduces the incidence of a composite of severe neonatal morbidities including at least one of bronchopulmonary dysplasia (BPD), retinopathy of prematurity (ROP), necrotizing enterocolitis (NEC), intraventricular hemorrhage (IVH) grades III/IV.
- c) To evaluate whether the effect of antihypertensive therapy for mild to moderate hypertension during pregnancy on primary outcome and SGA differs by a) prior antihypertensive therapy, b) racial-ethnic group, c) pre-existing diabetes, d) gestational age at randomization; e) maternal enrollment BMI.

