**CRL = Crown Rump Length** 

## 3.6 Study Groups

Randomization will be stratified by center, and there will be 2 intervention groups:

Group 1 (active treatment): 1st line antihypertensive therapy (labetalol or nifedipine ER supplied by the study) or other preferred medication (not supplied by the study) is started at the time of randomization. Treatment will be escalated to the maximum tolerated dose of a single agent prior to initiation of the preferred 2nd line medication (nifedipine ER or labetalol) to achieve target BP: <140/90.

Group 2 (standard comparison): This group will not receive antihypertensive therapy unless BP is ≥160 systolic or ≥105 diastolic (allowing a 5mmHg treatment buffer). If on antihypertensive therapy at the time of randomization, the antihypertensive therapy will be stopped at randomization. If pragmatic blood pressures reach ≥160 systolic or ≥105 diastolic, the lowest dose of labetalol or nifedipine ER needed to keep BP below this threshold will be started. (Based on available trials and systematic reviews, we estimate that 10% of women in this group will require BP treatment.) As part of routine clinical practice, providers will ask patients on medication about adherence before titrating the medication dose. In addition, research staff will monitor patient adherence through pill counts at the time of drug refills. Of note, if patients/providers prefer to use a medication other than nifedipine or labetalol according to protocol

after randomization, methyldopa or other appropriate antihypertensive may be used (however, this will not be provided by the study) and the patients will remain in the trial for the intent-to-treat analyses.

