#### 4.3 Randomization and baseline visit procedures

Randomization may occur upon confirmation that all inclusion/exclusion criteria are satisfied and after verification of participant consent and HIPAA authorization. Of particular importance, careful consideration will be given the patient's prior history of CHTN, current use of and adherence to antihypertensive therapy, and standardized clinic BP measurement to determine eligibility and the appropriate study algorithm to follow (see below). Study staff will also verify participant contact information and obtain a Release of Information, as permitted by local policy, to collect outcome and serious adverse event (SAE) documentation. Patients will be assigned to treatment groups with a concealed randomization allocation sequence using a web-based application managed by the Data Coordinating Center (DCC). Randomization will be stratified by clinical center to assure balance between treatment groups with respect to anticipated differences in the center population and possible differences in patient management. There will be 2 categories of patients with new or known mild chronic hypertension randomized:

a) Women with untreated CTHN: This group includes women with a new diagnosis of CHTN as well as women with a prior diagnosis of CHTN but not being treated. All of these patients must have pragmatic

clinic BP 140-159/90-104 to be eligible for randomization. (\*\*Note that criteria for a new diagnosis of chronic hypertension includes elevated BPs on at least 2 occasions a minimum 4 hours apart; a diagnosis of known chronic hypertension is based on current or prior antihypertensive therapy for a diagnosis of chronic hypertension).

- b) Those on a single antihypertensive agent who are adherent with their meds:
  - Adherent with medications defined as having taken medication within the last 24 hours of randomization.
  - BP inclusion range will be standardized pragmatic SBP ≤159 and DBP ≤104 for a woman in this group (including those with BP<140/90).

The enrollment BPs will be based on the single blood pressure <140/90 or the repeat blood pressure measurement (if ≥140/90) for clinical decision making (pragmatic clinic BP).

If a pragmatic clinic BP is not available for any reason, the automated/OMRON BP may be used to determine entry.

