#### 4.4 Participant Management

#### 4.4.1 Clinical management

A limited predefined management protocol will enhance the success of this pragmatic trial:

- A summary of the research management algorithm for patients in each of the two study groups will be strategically posted at clinic locations and will be placed in each participant's medical record; trained clinical (or research) staff will be available to measure pragmatic clinic BP at each visit.
- Routine pregnancy care at each center will be given to patients by clinical providers trained in the study protocol.

- Prescribed antihypertensive therapy according to study protocol will be supplied by the research team or designated pharmacist at each center/site until at least the time of delivery. After delivery the study medication or another appropriate antihypertensive agent will be used for at least 2 weeks after delivery.
- Prenatal visits will generally occur per local clinical standards at each site: every 1-3 weeks until 32-34
  weeks gestation when weekly or more frequent visits will be indicated (depending on antenatal testing
  initiation policy) at the discretion of the provider.
- After 20 weeks, standard clinical care suggests that preeclampsia should be excluded by a clinical diagnostic work-up (including urine protein, serum creatinine, CBC and liver enzymes as necessary) and adherence to therapy considered before enrolling patients or escalating dose due to elevated BP.
- Patients will receive lifestyle modification counseling per the routine clinical practice at each center for any
  patient with hypertension (nutrition counseling, exercise/physical activity advice and smoking and/or alcohol
  cessation interventions).
- Ultrasound for anatomy or fluid/growth and antenatal testing will be per clinical center's routine.
- Timing of delivery preferably no earlier than 38-39 completed weeks unless indicated earlier for obstetric or medical reasons according to local guidelines (consistent with ACOG recommendations)

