3.1.2. Analysis Plan: This hypothesis examines the effectiveness of structured blood pressure treatment (Lower BP group) for mild chronic hypertension in pregnancy versus usual care (Standard BP group). The  $\chi^2$  test of association will be used to evaluate whether the rate of the primary outcome differs between the two blood pressure management approaches. The primary analysis will follow an intention-to-treat (ITT) approach of all individuals randomized to the two treatment groups, regardless of whether they adhered to their assigned treatment. For cases where the primary composite outcome is undetermined (for example, dropout prior to delivery), the primary analysis will utilize multiple imputation for the primary outcome. Missing values will be estimated using characteristics within each treatment group that may be predictive of the composite outcome. Specifically, a logistic regression model will be fit within treatment group using baseline characteristics including diabetes status (yes/no), treatment status at enrollment (on BP meds vs. not on BP meds), age, BMI, and elevated BP at the first visit (SBP  $\geq$  150 and/or DBP  $\geq$  100). Multiple imputed data sets will be developed and up to 5 replicates will be considered. The primary analysis will be conducted on each of the imputed complete data sets and the final results will be pooled.

A sensitivity analysis will include all individuals for whom a primary outcome can be assessed (a complete-case analysis) in a modified ITT approach. Our expectation is that on a small fraction (<10%) of the dataset will require imputation and thus the complete case analysis will agree substantially with the primary imputation-based analysis.

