### 4. Additional Analyses

For the primary outcome, both intent-to-treat (as the primary) and a per-protocol approach will be used. The per-protocol population will be defined as those individual in the Lower BP (treatment) group who have >80% compliance and attendance at all scheduled visits. No adjustments will be made in the Standard Group since this provides our pragmatic control group. Secondary analyses will be examined accounting for the duration of therapy, prior antihypertensive therapy, race/ethnicity, pre-existing diabetes, GA at initiation of therapy and other covariates.

Pre-pregnancy and/or early pregnancy BMI will be evaluated for possible effects on all outcomes. Sensitivity analyses will be conducted to examine these possible effects. We will also evaluate potential interactions between BMI and treatment assignment. Subgroup analyses (by BMI class) will be explored where warranted. Similar interactions with other key patient characteristics will be examined.

Event free survival for the first occurrence of any of the primary outcome composite variables and will be calculated using Kaplan Meier estimates with testing via a log rank test. Student's t-test for comparisons of continuous outcomes (duration of hospital, NICU stay, etc.) will be conducted as well as regression analyses adjusting for pertinent covariates.

4.1 Secondary Aims/Hypotheses: Secondary outcomes will be compared using methods and approaches outlined above. The incidence of each of the 3 outcomes for this aim (perinatal death, composite neonatal morbidity, and composite of severe maternal morbidity) will be compared by completed weeks. To investigate the impact on the timing of delivery, longitudinal analysis of the full trial cohort with treatment arm as a key covariate, using completed gestational age (weeks 36-40) and their interaction as the independent variable will be implemented to assess the incidence of each of the 3 outcomes. The OR (95% CI) at each gestational age relative to 39 weeks will be computed and then adjusted for relevant covariate characteristics using logistic regression. Additional analyses will involve computing the adjusted OR and 95% CI for each outcome given delivery at a specific gestational age vs. at term. We will assess whether there is a gestational age beyond which waiting to deliver might be harmful.

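### Follow-up models adjust the arm comparison for duration of therapy and gestational age at its initiation, both shaped after randomization; baseline covariates and center should be used instead

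*Combined protocol and SAP*

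**What the plan says.** **Follow-up models.** After the chi-square test and risk ratio for the composite and SGA, protocol 5.3.1 adds "a logistic regression comparison which will take into account the duration of therapy, GA at initiation of therapy and other covariates". SAP section 4 (Additional Analyses) states: "Secondary analyses will be examined accounting for the duration of therapy, prior antihypertensive therapy, race/ethnicity, pre-existing diabetes, GA at initiation of therapy and other covariates".

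**When therapy starts.** Under protocol 3.6 the active (Lower) group starts at randomization. In the Standard group any existing therapy is stopped then, and "This group will not receive antihypertensive therapy unless BP is ≥160 systolic or ≥105 diastolic". For that group "we estimate that 10% of women in this group will require BP treatment". Protocol 5.1.1 and SAP 3.1.3 allow up to a further 10% treated outside the rule.

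**Center.** Protocol 4.3: "Randomization will be stratified by clinical center to assure balance between treatment groups with respect to anticipated differences in the center population". The primary test is nevertheless the plain chi-square; in SAP 3.1.2 this "test of association will be used to evaluate whether the rate of the primary outcome differs between the two blood pressure management approaches". SGA (SAP 3.2.2) and the interim and final boundaries (protocol 5.3.3, SAP 3.3) use the same statistic. Site enters only the adjusted model used on imbalance, the Breslow-Day check and a possible GEE.

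**Covariates.** SAP section 2 takes covariates from baseline tests at the 0.05 level. SAP 3.1.2 adjusts for those found imbalanced and names modified Poisson regression only as something to be considered.

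**The concern.** (a) Adjusting a randomized comparison for a variable that the allocation or the outcome can change no longer estimates the randomized effect. Duration of therapy ends at delivery in both arms, and indicated birth before 35 weeks is a component of the composite. An event therefore shortens the covariate. GA at initiation of trial therapy is a baseline value in the Lower group. In the Standard group it is a later value driven by rising BP, or does not exist. No rule says how to code women who never start. An adjusted odds ratio printed beside the primary risk ratio could then suggest harm or benefit that is not there.

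(b) and (c) are not errors. The plain chi-square remains valid, but it leaves unused the information for which randomization was stratified. Selecting covariates by baseline p-value responds to chance rather than to prognostic value, and leaves no single adjusted estimate designated in advance.

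**Working it through.** **The plan's own figures.** With a 33% reduction, the Lower rate is 16 × 0.67 = 10.72%. The pooled-variance two-proportion formula (two-sided 0.05, 85% power) gives 745 per arm; the plan states 748. With 10% crossover each way:
- Standard: 0.9 × 16 + 0.1 × 10.72 = 15.47%
- Lower: 0.9 × 10.72 + 0.1 × 16 = 11.25%

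This gives 1164 per arm, or 1139 if the reduction is 1/3; the plan states 1142. Then 1142/0.95 = 1202. Power at 1142 per arm is 84.3% (0.33) or 85.1% (1/3). Chi-square values of 9 and 3.87 correspond to p = 0.0027 and 0.0492. The plan's figures hold, and none depends on the follow-up models.

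**(a) Who has a value.** If 10–20% of Standard women start trial-period therapy, 80–90% do not: 0.8 × 1142 = 914 to 0.9 × 1142 = 1028 women per arm.

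**(a) Null simulation, both written covariates, untreated women coded zero.** Assumptions: 2284 women; about 16% events in each arm; randomization at 8–23 weeks; all Lower women treated; about 19% of Standard women treated, more often the more severe, starting 1–16 weeks after randomization; non-event deliveries averaging 38 weeks. Odds ratios (OR) are for Lower.

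| Event pregnancies deliver earlier by | OR, both covariates | False rejection (300 trials) |
|---|---|---|
| 0 weeks | 0.73 | 33% |
| 1 week | 1.05 | 5% |
| 2 weeks | 1.59 | 50% |
| 3 weeks | 2.55 | 93% |
| 5 weeks | 7.5 | 100% |

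GA at randomization in their place gave 1.006, identical to the unadjusted value.

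**(a) Null simulation, untreated Standard women dropped.** Assumptions: 1142 per arm; 16% events in both; 90% of Lower and 10 or 20% of Standard women treated; 25, 50 or 77% of events delivered before 35 weeks (77% = 12.32/16 from protocol 5.1.1); an odds ratio of 1 to 5 linking severe BP to the outcome; other deliveries at 38–39 weeks, following "Timing of delivery preferably no earlier than 38-39 completed weeks unless indicated earlier for obstetric or medical reasons". There were 500 trials per setting.
- Both covariates: OR 0.60–0.91 if severe BP is unrelated to outcome; 0.19–0.49 if its odds ratio is 2–5.
- GA at initiation alone: 0.68–0.95 and 0.18–0.50.
- GA at randomization alone: 0.99–1.01, with false rejection of 3–7%.

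A further null simulation of the two-covariate model, with its own assumed timing, gave 1.29–3.63 (coded zero), 0.40–1.05 (dropped) and 0.98–1.03 (GA at randomization alone).

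The mechanism fits. With zero coding, early-delivering events link short duration to the outcome, and the arm term offsets this upward. With dropping, the Standard women who remain are those whose BP rose.

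**(b) Center.** The statistic is CMH = [Σ(a_k − E_k)]²/ΣV_k, where a_k is the number of Lower events in center k and E_k and V_k are its hypergeometric mean and variance. Power (%) at 1142 per arm, final look, 40,000 trials, with center sizes and the SD of center log-odds assumed:

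| SD | 16 centers: chi-square → CMH | 30 centers: chi-square → CMH |
|---|---|---|
| 0 | 84.2 → 84.2 | 84.1 → 84.1 |
| 0.25 | 84.0 → 84.2 | 84.6 → 84.7 |
| 0.5 | 84.6 → 85.1 | 84.4 → 85.0 |
| 0.75 | 85.2 → 86.5 | 84.9 → 86.1 |

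A separate run at SD 1.0 gained at most about 1.6 points. Two-look type I error at 9 and 3.87 was 4.1–5.0% (chi-square), 4.8–5.1% (CMH) and 4.7–5.1% (chi-square at interim, CMH at final).

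**(c) Screening at 0.05.** For the six candidates in protocol 5.3.1, taken as independent, P(at least one flag) = 1 − 0.95⁶ = 26.5%. For 10, 20 or 30 tests (the number is not stated) it is 40%, 64% or 79%. Each covariate is left out 95% of the time, however prognostic it is.

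**The case against.** Several counter-arguments have force.

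- *Reach.* Protocol 5.3 defers detail to the SAP, whose main adjusted model (3.1.2) holds only group, site and imbalanced covariates. Duration appears only in SAP section 4. This stands: the defect is confined to follow-up and secondary models. A reader might infer that the consistency check closing SAP 3.1.2 covers these models too. It follows the missing-data analyses, and the text does not extend it to section 4.
- *Direction.* A reader might infer that the models must show harm in the Lower group. They need not: the simulated odds ratio falls on either side of 1 according to coding and delivery timing. No SGA simulation was run, so for SGA the point rests on reasoning alone.
- *Meaning of initiation.* It may be loose wording for GA at randomization, or may predate randomization for women already on monotherapy at entry. Both are possible. However, protocol 5.3.1 lists gestational age at baseline separately, and either reading still needs the text corrected. Duration is a defect on any reading.
- *Covariate list partly present.* SAP section 4 already lists prior therapy, race/ethnicity and diabetes without an imbalance trigger, and evaluates BMI. This stands, and it makes (c) a smaller step.
- *Center is a preference, changed mid-trial.* The gain is small. Table 9 puts enrollment at 59 + 405 + 503 + 134 + 122 = 1223 by mid-2018, so the interim cohort of 1202 was already enrolled. The worry about mixing statistics fails on the type I error shown above.

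**Conclusion.** (a) is wrong as written, for the follow-up and secondary models only. Under no true effect they can report spurious harm or spurious benefit, depending on a coding choice the plan does not state. The simulated odds ratios (0.73–7.5 coded zero, 0.19–1.05 dropped) are illustrative. They rest on assumed start and delivery times and an assumed link between severe BP and outcome, and leave out pre-trial therapy. What does not depend on those assumptions is that GA at randomization alone gives about 1.

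(b) and (c) are improvements. A reader might infer that the unstratified test is invalid; it is not, being only slightly conservative when centers differ. The gain from stratifying is about 0–1.6 power points, and zero if centers are alike. The primary intention-to-treat chi-square is sound throughout.

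**What to change.** **(a)** Remove duration of therapy and GA at initiation from every between-group model. Use GA at randomization and treatment status at entry. Report duration and initiation descriptively by arm, or in an analysis labelled non-randomized.

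**(b)** Analyze the composite and SGA with a center-stratified Mantel-Haenszel risk ratio and CMH test, pooling small centers by a rule fixed before unblinding. With multiple imputation, pool the stratified log risk ratio and use its squared Wald statistic (simulated two-look type I error 4.7–5.0% with 5% missing). Apply this only to looks not yet performed, at the stated 9 and 3.87. Keep the unadjusted chi-square as a sensitivity analysis.

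**(c)** Replace the p<0.05 trigger with one fixed list of baseline covariates the documents already name. An example is the protocol 1.3a set, where the aim asks whether the effect "differs by a) prior antihypertensive therapy, b) racial-ethnic group, c) pre-existing diabetes, d) gestational age at randomization; e) maternal enrollment BMI", plus baseline BP and center. Smoking or age could be added; what matters is fixing the list in advance. Name the modified Poisson risk ratio as the single adjusted estimate.

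**Cost.** Rewording of protocol 5.3.1 and 5.3.3 and SAP 2, 3.1.2, 3.2.2, 3.3 and 4. Protocol 1.4 requires Steering Committee and IRB approval, plus DSMB approval if the change is major. No extra patients or data are needed: protocol 5.2 lists entry GA, entry BP, treatment status, ethnicity and BMI as collected, and diabetes is in the SAP 3.1.2 imputation model.

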### 5.3.2 Secondary Aims

The secondary outcomes will be similarly compared. The incidence of each of the 3 outcomes for this aim (see 3.1.5 b ii) will be compared by completed weeks. To investigate the impact on the timing of delivery), longitudinal analysis of the full trial cohort with treatment arm as a key covariate, and completed gestational age (weeks 36-40) and their interaction as the independent variable will be implemented to assess the incidence of each of the 3 outcomes. The OR (95% CI) at each gestational age relative to 39 weeks will be computed and then adjusted for relevant covariate characteristics using logistic regression. Additional analyses will involve computing the adjusted OR and 95% CI for each outcome given delivery at a specific gestational age vs. at term. We will assess whether there is a gestational age beyond which waiting to deliver might be harmful.

